### **8.1 Distress from Return of Results**

Distress from return of results should be monitored at patient visits. If the participant seems overly distressed by the outcomes of the genetic test results, the Research Coordinator should:

1. Offer the participant the opportunity to speak to the genetic counselor. If the genetic counselor is not immediately available, the Research Coordinator should help coordinate a phone call or meeting with the genetic counselor based on participant's preference.
2. Inform the Project Manager who should then:
  - Inform PIs
  - Document the event in the notes field of the participant's study database record
  - Follow-up with participant

### **8.2 Events of Interest**

EHR data will be reviewed to monitor emergency department visits and hospitalizations. Sites will be asked to conduct two EHR data downloads, one after at least 25% of the participants have completed their 6 month visit, and another approximately 6-12 months after the last patient is randomized. EHR results will be sent to the IGNITE PTN CC via secure data transfer and formatted for data analyses. Details of the EHR download and transfer process will be provided separately to relevant site personnel.

### **8.3 Safety Monitoring/Data and Safety Monitoring Board**

The DSMB, appointed by the NHGRI, will be responsible for providing recommendations regarding the conduct of the study and guidance to ensure the safety and well-being of participants. The DSMB will meet semi-annually with one conference call and one in-person/virtual meeting. A DSMB Charter will be developed detailing the procedures to be followed. A Data and Safety Monitoring Plan and a separate DSMB statistical analysis plan (SAP) will be developed in collaboration with the IGNITE PTN, IGNITE PTN CC, and NHGRI, and enacted by the DSMB.

### **8.4 Early Termination and Participant Discontinuation**

Early termination considerations will generally apply only to emerging issues of major concern, or problems with trial conduct that suggest the trial could not be completed successfully with a reliable conclusion in a feasible time frame.

The site investigator, sponsor or institution may stop involvement of any participant in this research study at any time without their consent. This may be because the research study is being stopped, the instructions of the study team have not been followed, the investigator believes it is in the participant's best interest, or for any other reason. If specimens or data have been stored as part of the research study, they too may be destroyed without participant consent.

## 9. STATISTICAL ANALYSIS PLAN AND SAMPLE SIZE

### 9.1 Sample Size Determination

#### Main Study

In GUARDD, there was a 13% prevalence of *APOL1* positive individuals among hypertension participants and a standard deviation of 18.1 mm Hg for SBP. A separate unpublished pilot study from Indiana University showed a 20% prevalence of *APOL1* positive individuals among participants with CKD and an estimated CKD prevalence of 50%. Finally, another study showed a 26% prevalence of *APOL1* positive AAs with CKD. As such, the initial sample size determination assumed a 17% prevalence of *APOL1* positive individuals. However, observation of the prevalence of the *APOL1* positive study participants during the course of the study led investigators and the DSMB to believe that this assumption was too high and the actual prevalence in the study population was between 14 and 15 percent. Assuming a conservative 14% prevalence of *APOL1* positive individuals based on these studies, a sample size of approximately 6700 for the randomized population would result in approximately 938 *APOL1* positive individuals with at least 469 in each arm for the main study population examined here. Using a two tailed t-test and assuming an overall 5% level of significance, 10% lost-to-follow up, two interim analyses, and a standard deviation of 18.1 mm of Hg, a sample size of 6700 for the randomized population and approximately 938 for the *APOL1* positive individuals will detect a 3.5 mm Hg difference in the change in SBP from baseline to 3 months between Intervention - *APOL1* positive and Control - *APOL1* positive groups with at least 80% power. This sample size determination assumes 10% of the 938 *APOL1* positive individuals could drop out of the study before 3 months and therefore have incomplete data on SBP change from baseline to 3 months. *APOL1* positive individuals with incomplete data on SBP change from baseline to 3 months cannot be included in the primary endpoint analysis. Therefore, the final analysis on the primary endpoint needs at least 844 *APOL1* positive individuals who have complete data for SBP change from baseline to 3 months to detect a 3.5 mm Hg difference between two treatment groups. Enrollment will continue until the 844 target can be ensured. Since *APOL1* and SBP data could be missing for various reasons, approximately 50 additional participants will be randomized to help us to reach this 844 target. This makes the total randomization target to be approximately 6750. Enrollment may end prior to the 6750 target if the study team is certain that the necessary 844 *APOL1* positive individuals with complete SBP change data can be achieved.

#### PGx Substudy

Of the approximately 6750 participants in the GUARDD-US study, approximately 4400 will also be at a site participating in the PGx substudy. A sample size of 4400 with a 14% prevalence of *APOL1* positive individuals would result in 1892 participants for the PGx substudy (Intervention – *APOL1* negative participants) with 946 participants in the PGx Control and PGx Intervention arms. Using a two tailed t-test and assuming a 5% level of significance, 10% lost-to-follow up, and a standard deviation of 20 mm Hg (obtained from an unpublished study from the University of Florida), a sample size of 4400 for the randomized population and 1892 for the PGx substudy will detect a 3.1 mm Hg difference in the change in SBP from baseline to 3 months between the PGx Intervention group and PGx Control group with approximately 90% power.

## **9.2 General Statistical Methods**

A detailed SAP will be developed and contained in a separate document. Prior to analysis, study population details including the number randomized, in each treatment arm, and lost to follow-up will be described. Baseline participant characteristics will be summarized as means, standard deviations, medians, and/or 25th, 75th percentiles for continuous variables, and as counts and percentages for categorical variables. Model assumptions will be examined prior to analysis and transformations implemented, if necessary, to more adequately meet the assumptions. Unless otherwise stated, hypotheses will be tested as two-sided with a significance level of 0.05.

## **9.3 Population for Analyses**

### Population for Main Study Objectives

Participants from the Randomized Population who test positive for *APOL1*.

### Population for PGx Substudy Objective

Participants from the PGx substudy participating sites who are randomized to Intervention in the main study and test negative for *APOL1* are included in the PGx substudy population. Only participants who have non-missing PGx test results are included in the population for the primary and secondary analyses.

## **9.4 Analysis of the Primary Endpoint**

To determine the effect of knowledge of a positive *APOL1* status on SBP, we will compare the change in SBP from baseline to 3 months of the Intervention – *APOL1* positive group to the change in SBP from baseline to 3 months of the Control - *APOL1* positive group using a two sided t-test with an overall two-sided type I error of 0.05. Participants that are *APOL1* negative in both the Intervention and Control groups will not be included. This primary analysis will be conducted according to the principle of intention-to-treat (ITT) with participants analyzed and endpoints attributed according to the treatment arm to which the participants were randomized, regardless of subsequent crossover or post-randomization medical care within the pre-specified subset of *APOL1* positive participants.

## **9.5 Analysis of the Secondary Endpoints**

The effect of knowledge of a positive *APOL1* status on secondary endpoints [i.e., change in urine microalbuminuria/proteinuria orders from baseline to 6 months (Y/N), documented order of microalbuminuria/proteinuria tests by 6 months (Y/N), change in documented diagnosis for stage 3 CKD and above (Y/N) from baseline to 6 months, documented diagnosis of CKD stage 3 and above by 6 months (Y/N), change in documented diagnosis for any stage CKD from baseline to 6 months (Y/N), and documented diagnosis of all stages of CKD by 6 months (Y/N) ] will be compared between Intervention - *APOL1* positives and Control - *APOL1* positives with the proportion difference test.

## **9.6 Other Planned Analyses**

Trends in SBP. In addition to the primary endpoint analysis described above, we will compare the time trends in SBP between Intervention – *APOL1* positive individuals and Control – *APOL1* positive individuals using a repeated measures mixed model. Since participants are randomized to Intervention and Control groups and not to the *APOL1* positive subgroups within Intervention and Control groups, there could be important differences in baseline characteristics between the two groups. For this reason, we will conduct covariate-adjusted repeated measures mixed models that will account for differences in baseline characteristics that differ between the Intervention – *APOL1* positive group and the Control – *APOL1* positive group. Potential baseline covariates include baseline SBP, age, sex, and baseline CKD. We will select the appropriate covariance matrix (e.g.,

compound symmetry, autoregressive, unstructured, or other covariance structure) based on the data to account for repeated measures.

CKD subset. If the data provide evidence of an overall difference in the primary outcome (change in SBP from baseline to 3 months) between Intervention – *APOL1* positive group and the Control – *APOL1* positive groups, we will further examine whether the effect of knowledge of a positive *APOL1* status on SBP differs among those with and without CKD. This subgroup analyses will involve testing for interactions between treatment arm and CKD using linear regression. Effect estimates will be carefully (conservatively) interpreted in conjunction with the formal interaction test. If the interaction is significant, we will test whether the time trends in effect of early versus delayed knowledge of a positive *APOL1* status on SBP differs among Intervention – *APOL1* positive group and the Control – *APOL1* positive groups in those with CKD at baseline using a covariate-adjusted repeated measures mixed model. Potential covariates are the same as described above. We will select the appropriate covariance matrix (e.g., compound symmetry, autoregressive, unstructured, or other covariance structure) based on the data to account for repeated measures.

Controlled versus Uncontrolled Blood Pressure Subset. We will also examine whether the effect of knowledge of a positive *APOL1* status on SBP differs among those whose blood pressure is well-controlled at baseline versus those whose blood pressure is not well-controlled at baseline. This subgroup analyses will involve testing for interactions between treatment arm and whether or not SBP is 140 mm Hg or greater at baseline using linear regression. Effect estimates will be carefully (conservatively) interpreted in conjunction with the formal interaction test. As an additional subgroup analysis, we will similarly examine the effect of knowledge of a positive *APOL1* status on SBP between those on treatment for hypertension versus those not on treatment in the subset of participants with SBP 140 mm Hg or greater.

Cost-Effectiveness (CE). Complete details of the cost-effectiveness analysis (CEA) will be presented in a separate SAP depending on the outcome of the main study. Briefly, two analyses will be conducted comparing economic outcomes in Intervention – *APOL1* positive and the Control – *APOL1* positive groups. In the first, *within-trial cost analysis*, 6-month total healthcare cost will be estimated per participant using estimates of intervention costs (obtained from Centers for Medicare and Medicaid Services (CMS) physician fee schedule), medication costs (obtained from participant survey, EHR costs per cost center and/or total costs, VAFFS drug prices, National Average Drug Acquisition Cost (NADAC) drug prices, Medicare drug prices), and downstream health care costs of inpatient, outpatient, and emergency department use (from participant survey, EHR costs per cost center and/or total costs, Medicare outpatient prospective payment system (PPS) for healthcare common procedure coding system (HCPCS), cost-to-charge-ratio (CCR) for estimating inpatient costs from charges). The analyses will be adjusted for baseline 3-month total costs and utility scores by means of regression. The second, *long-term CE analysis*, will use a microsimulation model with five health states (Well, Cardiovascular Disease (CVD), ESRD, CVD plus ESRD, and Death) for predicting CE outcomes over a 5-year, 10-year and lifetime horizon following U.S. recommendations. The microsimulation model's predictions of CVD, ESRD and competing mortality rates will be informed by published epidemiological risk models and U.S. life tables. Specifically, we will use the Pooled Cohort Equations for modeling CVD and epidemiological studies for linking CKD stage to long-term ESRD risk with the following risk factors as input parameters: participant demographics (age, gender, and race) obtained from participant surveys; 6-month systolic blood pressure measurements; 6-month smoking status and preventive medication use (BP med) obtained from participant surveys; and 6-month diabetes status, eGFR, urine albumin to creatinine ratio, and blood cholesterol parameters obtained from the EHR. The estimated event rates of CVD, ESRD and competing mortality will be modified using expected rate ratios of blood pressure lowering therapy estimated from difference in 6-month change of systolic blood pressure from baseline. Rate ratios will be based on published meta-analyses of trials on blood pressure lowering medication. The microsimulation model will be used to estimate cumulative costs and QALYs as a function of life expectancy and simulated CVD and ESRD events for each trial participant. Long-term utility and cost penalties

conditioned on increasing age, CVD, and ESRD will be based on the literature. Details of the procedures for obtaining EHR data and estimates from the EHR will be provided in the MOP and SAP.

**PGx Substudy.** Analyses for the PGx substudy will compare outcomes between *APOL1* negative individuals with immediate PGx ROR (PGx Intervention) and *APOL1* negative individuals with delayed PGx ROR (PGx Control). A two sided t-test with a two-sided type I error of 0.05 will be used to evaluate differences in the change in SBP from baseline to the 3 month study visit between PGx Intervention and PGx Control groups. To evaluate time trends in SBP, we will also conduct covariate-adjusted repeated measures mixed models that will account for differences in baseline characteristics that differ between the PGx Intervention group and the PGx Control group. Potential baseline covariates are as described above. We will select the appropriate covariance matrix (e.g., compound symmetry, autoregressive, unstructured, or other covariance structure) based on the data to account for repeated measures. Additional exploratory endpoints and analyses for the PGx substudy will be described in a separate SAP.

Details of these statistical analyses along with all other exploratory analyses (e.g., mediators, moderators and psychobehavioral impact of results disclosure on participant outcomes and provider treatment recommendations, and medication adherence) will be described in the study SAP.

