#### **4.3 Blinding**

GUARDD-US randomization assignments will not be blinded to any participants, providers or study personnel because: 1) it is impossible to mask participants from the intervention testing and ROR, 2) research staff often receive questions from participants about the interpretation and risk associated with the participant's genetic results during the administration of surveys, and 3) resource limitations make hiring additional blinded staff to measure blood pressure impractical. To minimize bias in the measurement of the primary outcome, randomization assignments will only be revealed after baseline survey responses and blood pressure readings have been collected, digital blood pressure devices (such as Professional Intellisense Blood Pressure Monitor OMRON-907) will be used to measure blood pressure, and blood pressure will be measured as the mean of the second and third blood pressure readings for each participant at each visit. Manual blood pressures may be collected if necessary.

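### The exploratory SBP mixed models (main trend and PGx) pick covariates by observed imbalance, so baseline SBP would usually be left out and precision given up

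*Combined protocol and SAP*

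**What the plan says.** Section 9.6 (Trends in SBP) first plans a repeated measures mixed model comparing SBP over time between the two APOL1-positive groups. It then argues that, because randomization was to arms and not to the APOL1-positive subgroups, "there could be important differences in baseline characteristics between the two groups". It therefore adds "covariate-adjusted repeated measures mixed models that will account for differences in baseline characteristics that differ between the Intervention" and Control APOL1-positive groups. No criterion is given for deciding that a characteristic differs. The candidates are left open: "Potential baseline covariates include baseline SBP, age, sex, and baseline CKD". On the correlation structure it says "We will select the appropriate covariance matrix", to be chosen from the data, with several options and no default.

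The PGx paragraph of Section 9.6 repeats the rule: its models will "account for differences in baseline characteristics that differ between the PGx Intervention group and the PGx Control group". The CKD-subset paragraph reuses the list of potential covariates and the covariance wording, but does not repeat adjustment for characteristics that differ.

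The primary analysis in Section 9.4 is a separate, unadjusted two-sided t-test on the 3-month change. Section 9.8 calls the repeated measures analyses exploratory. Section 9.9 keeps p-values for the primary endpoint and reports secondary analyses as estimates with 95% confidence intervals.

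**The concern.** The stated reason does not hold. APOL1 genotype is fixed before randomization, so APOL1-positive Intervention and APOL1-positive Control participants form a randomized comparison. The same is true of PGx: Section 4.2 assigns the PGx arm at the same time as the main arm, before genotype is known. Observed baseline differences are then chance. The exception is selective missingness, for example because Control samples are genotyped only after the 6-month visit (Section 7.5).

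Selecting covariates by observed imbalance asks the wrong question. A covariate improves the estimate because it predicts the outcome. A strongly predictive covariate that happens to be balanced would be dropped, and under randomization balance is the usual result. The covariate most likely to matter for SBP is baseline SBP, and the rule would leave it out in most realizations of the trial. What is at stake is the width of the intervals for the exploratory SBP models.

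**Working it through.** **Inputs from the documents.** Section 9.1: 844 evaluable APOL1 positives (422 per arm), SD 18.1 mm Hg, difference 3.5 mm Hg, 80% power, 10% loss. Section 9.7: final level 0.0492 for the primary endpoint, critical value 1.967. That level does not govern the mixed models; power is used here only as a yardstick for precision.

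**Assumptions, not in the documents.** The correlation r between baseline and follow-up SBP is 0.4 to 0.7. A covariate counts as different at p<0.05, with p<0.10, p<0.20 and an absolute standardized mean difference (SMD) above 0.1 as alternatives. The arithmetic uses one follow-up time as a simplification of the mixed model.

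**Step 1: reproduce the plan.** n per arm = 2 × 18.1² × (1.967 + 0.842)² / 3.5² = 422, so 844 in total, and 844 / 0.9 = 938. Both match Section 9.1. The standard error is 18.1 × √(2/422) = 1.246 and power is 80.0%.

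**Step 2: covariate always entered.** If 18.1 is the SD of change and the variance is equal at both visits, baseline SBP explains R² = (1 − r)/2 of the variance of change: 0.15 at r = 0.7 and 0.30 at r = 0.4. The standard error becomes 1.246 × √(1 − R²).

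| R² | Standard error | 95% CI half-width | Narrower by | Power |
|---|---|---|---|---|
| 0 | 1.246 | 2.44 | – | 80% |
| 0.15 | 1.149 | 2.25 | 8% | 86% |
| 0.30 | 1.043 | 2.04 | 16% | 92% |

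The narrowing is 1 − √(1 − R²), which does not depend on n or SD, so it carries over to PGx at the same R². If 18.1 is instead the SD of follow-up SBP and that is the response, R² = r² and power when always adjusted is 86% to 97% for r = 0.4 to 0.7.

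**Step 3: covariate entered only if it differs.** Under randomization a covariate is selected in 5%, 10% and 20% of trials at p<0.05, p<0.10 and p<0.20, and in 14.6% at SMD above 0.1 with 422 per arm. In all other trials the interval keeps its unadjusted width. Simulation at p<0.05 (20,000 replicates) gave:

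| R² | Never adjusted | Only if different | Always adjusted |
|---|---|---|---|
| 0.15 | 79% | 80% | 86% |
| 0.30 | 80% | 81% | 92% |

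A separate simulation (6,000 trials per setting, r = 0.4 to 0.7, both responses) gave the share of the power gain kept: 11–15% at p<0.05, 19–23% at p<0.10, 31–36% at p<0.20 and 23–28% at SMD above 0.1.

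Measured by the variance of the estimate across trials, the share kept at a z threshold c is 2[cφ(c) + 1 − Φ(c)]. At c = 1.96 this is 2[0.1146 + 0.025] = 0.279, so 72% is lost. The loss is 56% at p<0.10, 45% at SMD above 0.1 and 35% at p<0.20.

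**Step 4: type I error.** Applied mechanically at p<0.05, the rule gave 4.65% at R² 0.15 and 4.1% at R² 0.30. It is conservative.

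**Step 5: limit of the approximation.** If all three visits are responses with separate means by arm and visit, and data are complete, a covariate entered as a time-constant main effect cancels from the change contrast. A check gave a standard error of 1.246 with and without it. The gain in Step 2 therefore comes from baseline SBP, entered as a covariate for later visits or as a first response with a common mean across arms. Age, sex or CKD as main effects add little to a visit contrast.

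**The case against.** The strongest reply is that these models are exploratory, carry no p-values, and are to be detailed in a separate SAP (Sections 9.2 and 9.6). The threshold and correlation behind the figures are also assumptions. At an R² of 2–5%, always adjusting lifts power only from 80.0% to 81–82%. On across-trial variance, less than half of the gain is lost at p<0.20 or SMD above 0.1. All of this stands and limits the size of the point. It does not rescue the rule: the text already states how covariates are chosen, and a SAP that follows Section 9.6 would inherit it.

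Selective missingness could produce real differences. Even then, testing for imbalance is a poor way to choose covariates, and a fixed set serves better.

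A reader might infer three stronger points that the documents do not support:

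- **Inflated error.** Section 4.3 says "randomization assignments will not be blinded to any participants, providers or study personnel", and picking the most favourable of the 16 subsets of the four named covariates gave type I error of 8.6–10.5% at nominal 5% under illustrative effects. No such search is planned, and Section 4.3 does not say how the model would be selected. The stated rule, followed mechanically, is conservative.
- **All SBP models share the rule.** The CKD-subset paragraph repeats the candidate list and covariance wording only.
- **Data-based covariance choice biases the result.** This was not quantified. It is a request for pre-specification.

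**Conclusion.** The point holds for the main-trend and PGx mixed models. The reason given for the rule is mistaken, and the rule usually omits baseline SBP. Under an assumed R² of 0.15–0.30, a p<0.05 threshold and a single follow-up, it keeps about one of the 6 to 12 available points of power and usually forgoes an interval 8–16% narrower. Most of the power gain is lost at every threshold tried, though less at looser ones, and there is little to lose if the covariate is weak. The loss concerns baseline SBP; it should not be read as a gain forgone for each named covariate.

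The primary t-test, its error rate and the 844 and 938 targets are unaffected. The change is worth making because it costs almost nothing; it does not threaten the trial's main conclusion.

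**What to change.** In Section 9.6, delete adjustment for observed differences from the Trends in SBP and PGx paragraphs, together with the subgroup argument that supports it. In its place, state that:

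- The main and PGx SBP models always include baseline SBP, age, sex and baseline CKD, whatever the observed balance.
- Baseline SBP enters once: either as a covariate with 3- and 6-month SBP as responses, or as a first response with a common mean across arms.
- The CKD-subset model always includes baseline SBP, age and sex. Baseline CKD is constant there and cannot be estimated.

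As a minor addition, name unstructured covariance with a fixed fallback order for non-convergence. With three visits it has 3 × 4 / 2 = 6 parameters, which is modest for more than 800 participants.

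The cost is a few sentences in Section 9.6, mirrored in the SAP. The plan already names all four covariates, so no new data, visits or participants are needed.

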## 2. INTRODUCTION

### 2.1 Background, Significance, and Rationale

Chronic kidney disease (CKD) is associated with hypertension and diabetes and affects 26 million US adults. African Americans (AA's) have higher risk of end stage renal disease (ESRD) necessitating maintenance dialysis or transplant than Whites. This disparity widens as kidney function declines. Additionally, AAs have the highest prevalence of hypertension (41% AA, 28% White) and the lowest rate of blood pressure (BP) control (43% AA versus 53% White). While improved BP control decreases CKD progression and reduces morbidity and mortality, BP control (defined as < 140/90 mm Hg) is only achieved in 50% of participants.

One in 7 AAs carry the Apolipoprotein L1 (*APOL1*) gene risk allele, but it is nearly absent in other populations. High-risk variants in the *APOL1* explain approximately 70% of the excess prevalence of CKD in AAs, conferring a 5 times higher risk for hypertensive CKD and a 10 times higher risk for ESRD. This risk is conferred by two variants (G1 and/or G2) in the last exon of *APOL1* with the high-risk genotype being G1/G1; G2/G2 or G1/G2. *APOL1* does not significantly increase CKD risk in hypertensive people with diabetes and normal renal function, but in hypertensive people with prevalent CKD, *APOL1* exacerbates worsening of kidney function and progression to ESRD regardless of diabetes diagnosis. Among adults with CKD, specific medications (angiotensin-converting enzyme (ACE) inhibitors or angiotensin receptor blockers (ARBs)) are recommended for participants of all ancestries, but 50% of participants do not receive these medications. Compounding this issue is the fact that providers do not include CKD on the problem list of 40% of participants with lab evidence of CKD, leading to widespread participant unawareness of CKD. Urine protein tests, essential for early diagnosis and prognosis of CKD, are missing in up to 30% of participants with CKD.

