#### Participants

- An educational booklet given to all participants at the baseline visit that includes information about high blood pressure, kidney disease, and *APOL1* gene testing, and language recommending that participants speak with their provider if their BP is >130/80 mm Hg.
- The results of participant blood pressure readings at each study visit including
  - the mean of the second and third blood pressure readings
  - an indication of whether the mean value is normal (<130/80 mm Hg), up to your provider (between 131/81 mm Hg and 140/90 mm Hg) or elevated (>140/90 mm Hg)
  - a recommendation to speak with a provider if the participant's BP is above normal
- The verbal return of *APOL1* genetic testing results (i.e., *APOL1* positive or negative) and a verbal explanation of the meaning of the genetic testing results for risk of CKD and hypertension to participants following the schedule of activities and procedures for the participant's *APOL1* randomization assignment (see Section 7.10).
- A written explanation of the clinical implications of the patient's *APOL1* genetic testing results given to participants at the time of ROR.
- The same educational booklet will be given to participants as a reminder at the time of ROR.
- The option for patients to speak with a genetic counselor about their results.

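### Modification of the effect by baseline blood pressure is tested only by cutting baseline SBP at 140 mm Hg; an interaction with continuous baseline SBP should be added beside the cut

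*Combined protocol and SAP*

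**What the plan says.** Under the controlled versus uncontrolled subset, section 9.6 sets out to compare the effect of knowing a positive *APOL1* status between "those whose blood pressure is well-controlled at baseline versus those whose blood pressure is not well-controlled at baseline". It does so by "testing for interactions between treatment arm and whether or not SBP is 140 mm Hg or greater at baseline using linear regression". The same cut defines the group in which treated and untreated participants are then compared.

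Baseline SBP appears in one other place in section 9.6, as a possible adjustment variable in the time-trend models: "Potential baseline covariates include baseline SBP, age, sex, and baseline CKD". That is adjustment, not an interaction with arm. No arm by continuous baseline SBP term is written anywhere in the protocol. Section 9.6 leaves further detail, including moderators, to a separate study SAP that is not part of these documents.

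The documents give no power, information figure or expected subgroup sizes for this interaction.

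**The concern.** Baseline SBP is the mean of two readings under the study blood pressure protocol (section 10.2). Reducing it to an indicator treats participants at 139 and 141 as different kinds of people, and participants at 141 and 185 as the same. If the effect grows steadily with baseline pressure, much of the evidence for that growth lies within the two groups, and the indicator cannot use it.

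The question has substance here because eligibility sets no lower limit on SBP. Under section 5.1 a diagnosis code, active therapy or a problem-list entry is enough. Participants whose SBP is already below 140 can therefore enrol, and they have less room to fall. Interactions are also estimated imprecisely at this sample size, so avoidable loss matters. At stake is the precision and usefulness of a planned subgroup analysis, not the primary comparison.

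**Working it through.** **Inputs from the documents.** Section 9.1 gives SD 18.1 mm Hg, a target difference of 3.5 mm Hg, at least 80% power and 844 analysable *APOL1* positive participants, and states "Using a two tailed t-test and assuming an overall 5% level of significance". Section 9.7 gives a final significance level of 0.0492 for the primary endpoint. Section 9.2 sets two-sided 0.05 for other tests.

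**The plan's own figure.** Per arm, n = 2 x 18.1² x (1.967 + 0.842)² / 3.5² = 422, so 844 in total, and 844/0.9 = 938. Both agree with section 9.1. At 0.05 the result is 420 per arm.

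**Inputs not in the documents.** The baseline SBP distribution and the share p at or above 140 are not given. Section 2.1 offers background control rates only: "the lowest rate of blood pressure (BP) control (43% AA versus 53% White" and, overall, control that "is only achieved in 50% of participants". These would suggest p of 57% and 50%. But they are population rates for combined systolic and diastolic control, so the systolic-only share could be lower, and they are not trial data. I therefore use p from 30% to 70%.

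**Information kept by the cut.** For a normal modifier with linear modification, the share kept is R = φ(c)² / [p(1 − p)], where c is the normal quantile with a proportion p above it. If the continuous test has 80% power at two-sided 0.05, the power after the cut is Φ(2.80 x √R − 1.96).

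| Share at or above 140 | R | Loss | 844 participants worth | Power after the cut |
|---|---|---|---|---|
| 50% | 0.637 | 36.3% | 537 | 61% |
| 43% or 57% | 0.629 | 37.1% | 531 | 60% |
| 30% or 70% | 0.576 | 42.4% | 486 | 57% |

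The loss is smallest at an even split. Outside the range it is larger, for example 51% at p = 20%.

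**Simulation check.** The regression interaction test was simulated with 844 participants and 4,000 runs per scenario. The information ratio was 0.635 at p = 50%, 0.633 at 57% and 0.573 at 30%. At 57%, power was 79% for the continuous term and 60% for the cut. If baseline SBP also predicts the change in SBP (assumed slope −0.4 SD per SD), the loss at 57% rises to about 41%.

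**Other shape.** If the true modification is a step at 140, the indicator is the correct term and loses nothing. The linear term is then the weaker test: at p = 57%, 59% power against 80% for the cut.

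**Scale of the interaction.** With 844 analysed, the standard error of the change in effect per SD of baseline SBP is about 2 x 18.1/√844 = 1.25 mm Hg. Power of 80% therefore needs 2.80 x 1.25 = 3.5 mm Hg per SD. For an even split, the subgroup difference has a standard error of 1.25/0.5 = 2.5 mm Hg, and 80% power needs a difference of about 7 mm Hg.

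**The case against.** **A threshold is plausible.** Participants are told their reading is normal, intermediate "or elevated (>140/90 mm Hg", and provider alerts carry recommendations for elevated pressures. Behaviour triggered at a cut-point could produce a step, and replacing the indicator with a linear term would then lose power. This stands, and it is why the continuous term should be added and the cut kept.

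**The illustration needs a large interaction.** A change of 3.5 mm Hg per SD is as large as the whole target effect. At half that, power is about 29% on the continuous scale and 20% after an even split. This also stands: the change improves precision but does not make the test well powered.

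**The consequence is limited.** Section 9.9 confines p values to the primary endpoint, and section 9.6 promises cautious interpretation. The gain will therefore show mainly in estimates and intervals. The separate SAP may already contain a continuous analysis. All that can be said is that the protocol specifies none, while it does specify the cut.

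**Definition of control.** A reader might also infer that the systolic-only cut is an error, because section 2.1 has "BP control (defined as < 140/90 mm Hg", under which a participant at 135/95 is uncontrolled. The documents do not support that. Section 2.1 is describing population control rates, whereas section 9.6 states its own rule for a systolic endpoint. One hypertension criterion in section 5.1 also uses SBP 140 alone. Redefining the subgroups by 140/90 would be a debatable preference. At most, the labels should say what the cut is.

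**Conclusion.** The point holds as a low-cost improvement to a planned subgroup analysis. Under a roughly normal baseline SBP and linear modification, the split at 140 loses about 36-42% of the interaction information when 30-70% of participants are at or above the cut, and 80% power becomes about 57-61%. Under a step at 140 the loss is zero.

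A reader might take a single figure near 37% as a property of this trial. It is not: it comes from applying background control rates to an assumed distribution and an assumed shape of effect. Nor do the documents establish that baseline SBP is the most plausible modifier; they show only that the investigators chose to examine it. The primary test, its sample size and its significance level are unaffected.

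**What to change.** In section 9.6 or the study SAP, add an arm by continuous baseline SBP interaction within the same linear-regression analysis, linear in form and with a spline version as a check on shape. Report the estimated difference between arms over the range of baseline SBP, with 95% confidence intervals.

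Keep the prespecified split and its two subgroup estimates with 95% confidence intervals, labelled SBP <140 and SBP >=140 mm Hg. Fit the continuous and the binary interaction as separate models. Under the normal assumption the squared correlation between the two forms of baseline SBP is R (0.58-0.64), so the two terms would compete in one model. State beforehand that both are supportive, so that neither can be picked after the results are seen.

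The cost is SAP wording and one figure, with no new data. The downside is that a linear term can miss a threshold; the retained subgroup estimates and the spline check guard against that.
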